#### **4.4 Discontinuation/Withdrawal of Study Subjects**

The subject will be considered to have completed the study when she completes all scheduled Study Treatments and follow-up visits or death, whichever occurs first. The discharge visit will be the last follow-up visit. If subject discontinues or is withdrawn at any time after receipt of Study Treatment, the investigator should make every effort to have the subject complete all assessments designated for the discharge visit. The investigator will make every effort to have all scheduled immune assessment blood sample collected as indicated in the Schedule of Events, Table 1 of the Clinical Synopsis. Any adverse events (AEs) present at the time of discontinuation/withdrawal should be followed in accordance with the safety requirements outlined in Section 7.1 – Safety Parameters.

If the subject manifests Grade 4 toxicity attributable to study treatment/EP, she will not receive further study treatment/EP but will be encouraged to continue follow-up safety assessment through study discharge and not discontinue from the study. If a subject manifests Grade 3 toxicity attributable to study treatment/EP, the medical monitor and PI will discuss whether further treatment should be continued for that participant.

Subjects will be discontinued from the study if there is confirmed disease progression or if subject starts new anti-cancer therapy.

The reason for any discontinuation of study treatment should be discussed with the Sponsor's Medical Monitor within 24 hours. The primary reason for the subject discontinuing further study treatments or withdrawal from the study itself should be selected from the following standard categories:

- Adverse Event (Adverse Reaction): Clinical or laboratory events occurred that, in the medical judgment of the investigator for the best interest of the subject, are grounds for discontinuation. This includes serious and non-serious adverse events regardless of relation to study treatment.
- Death: The subject died.
- Withdrawal of Consent: The subject desired to withdraw from further participation in the study in the absence of an investigator-determined medical need to withdraw. If the subject gave a reason for withdrawal, it should be recorded on the Case Report Form (CRF). This reason does not allow for further data collection and should not be selected if follow-up data collection of this subject is anticipated by the subject.

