##### **6.2.4.1 Medical and Clinical Assessments**

New onset disease and concomitant medications will be collected on Day 0 and at all subsequent study visits through discharge.

Assessment of systemic reaction/toxicity/side effects of standard (chemoradiation) therapy will be collected at specified visits and be reported using the “Acute Radiation Morbidity Scoring Criteria (RTOG)”, (Appendix 5).

Assessment of all other adverse events will be collected from the time of informed consent through discharge and will be assessed using the CTCAE v4.03 issued by the US Department of Health and Human Services on June 14, 2010 (Appendix 4).

Clinical evaluations for disease response will be conducted at all of the study visits (as assessed by clinical signs and symptoms of disease progression). PET/CT scans for disease progression will be obtained for all subjects 3-5 months after Day 0 and every 3-5 months thereafter per standard of care or in accordance with local guidelines and institutional practices.

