#### **7.1.3 Severity Codes for AEs**

Study personnel will grade laboratory AEs and clinical AEs (based on discussions with study participants) with respect to the following levels of severity as defined in Common Terminology Criteria for adverse events (CTCAE) of the National Cancer Institute for reporting of all serious adverse events (SAE) or the Acute Radiation Morbidity Scoring Criteria (RTOG).

- Mild (Grade 1);
- Moderate (Grade 2)
- Severe (Grade 3);
- Potentially Life Threatening (Grade 4)
- Death (Grade 5)

A copy of the CTCAE version 4.03 is provided in Appendix 4 and may be downloaded from the CTEP home page (<http://ctep.cancer.gov/reporting/ctc.html>):

A copy of the Acute Radiation Morbidity Scoring Criteria can be downloaded from the Radiation Oncology Therapy Group home page (<http://www.rtog.org/ResearchAssociates/AdverseEventReporting/AcuteRadiationMorbidityScoringCriteria.aspx>).

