## Blood and lymphatic system disorders

Adverse Event	Grade				
	1	2	3	4	5
Anemia	Hemoglobin (Hgb) <LLN - 10.0 g/dL; <LLN - 6.2 mmol/L; <LLN - 100 g/L	Hgb <10.0 - 8.0 g/dL; <6.2 - 4.9 mmol/L; <100 - 80g/L	Hgb <8.0 g/dL; <4.9 mmol/L; <80 g/L; transfusion indicated	Life-threatening consequences; urgent intervention indicated	Death
Definition: A disorder characterized by a reduction in the amount of hemoglobin in 100 ml of blood. Signs and symptoms of anemia may include pallor of the skin and mucous membranes, shortness of breath, palpitations of the heart, soft systolic murmurs, lethargy, and fatigability.					
Bone marrow hypocellular	Mildly hypocellular or <=25% reduction from normal cellularity for age	Moderately hypocellular or >25 - <50% reduction from normal cellularity for age	Severely hypocellular or >50 - <=75% reduction cellularity from normal for age	Aplastic persistent for longer than 2 weeks	Death
Definition: A disorder characterized by the inability of the bone marrow to produce hematopoietic elements.					
Disseminated intravascular coagulation	-	Laboratory findings with no bleeding	Laboratory findings and bleeding	Life-threatening consequences; urgent intervention indicated	Death
Definition: A disorder characterized by systemic pathological activation of blood clotting mechanisms which results in clot formation throughout the body. There is an increase in the risk of hemorrhage as the body is depleted of platelets and coagulation factors.					
Febrile neutropenia	-	-	ANC <1000/mm  with a single temperature of >38.3 degrees C (101 degrees F) or a sustained temperature of >=38 degrees C (100.4 degrees F) for more than one hour.	Life-threatening consequences; urgent intervention indicated	Death
Definition: A disorder characterized by an ANC <1000/mm  and a single temperature of >38.3 degrees C (101 degrees F) or a sustained temperature of >=38 degrees C (100.4 degrees F) for more than one hour.					
Hemolysis	Laboratory evidence of hemolysis only (e.g., direct antiglobulin test; DAT; Coombs'; schistocytes; decreased haptoglobin)	Evidence of hemolysis and >=2 gm decrease in hemoglobin.	Transfusion or medical intervention indicated (e.g., steroids)	Life-threatening consequences; urgent intervention indicated	Death
Definition: A disorder characterized by laboratory test results that indicate widespread erythrocyte cell membrane destruction.					

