Colonic perforation	-	Symptomatic; medical intervention indicated	Severe symptoms; elective operative intervention indicated	Life-threatening consequences; urgent intervention indicated	Death
Definition: A disorder characterized by a rupture in the colonic wall.					
Colonic stenosis	Asymptomatic; clinical or diagnostic observations only; intervention not indicated	Symptomatic; altered GI function	Severely altered GI function; tube feeding or hospitalization indicated; elective operative intervention indicated	Life-threatening consequences; urgent operative intervention indicated	Death
Definition: A disorder characterized by a narrowing of the lumen of the colon.					
Colonic ulcer	Asymptomatic; clinical or diagnostic observations only; intervention not indicated	Symptomatic; altered GI function	Severely altered GI function; TPN indicated; elective operative or endoscopic intervention indicated; disabling	Life-threatening consequences; urgent operative intervention indicated	Death
Definition: A disorder characterized by a circumscribed, inflammatory and necrotic erosive lesion on the mucosal surface of the colon.					
Constipation	Occasional or intermittent symptoms; occasional use of stool softeners, laxatives, dietary modification, or enema	Persistent symptoms with regular use of laxatives or enemas; limiting instrumental ADL	Obstipation with manual evacuation indicated; limiting self care ADL	Life-threatening consequences; urgent intervention indicated	Death
Definition: A disorder characterized by irregular and infrequent or difficult evacuation of the bowels.					
Dental caries	One or more dental caries, not involving the root	Dental caries involving the root	Dental caries resulting in pulpitis or periapical abscess or resulting in tooth loss	-	-
Definition: A disorder characterized by the decay of a tooth, in which it becomes softened, discolored and/or porous.					
Diarrhea	Increase of <4 stools per day over baseline; mild increase in ostomy output compared to baseline	Increase of 4 - 6 stools per day over baseline; moderate increase in ostomy output compared to baseline	Increase of >=7 stools per day over baseline; incontinence; hospitalization indicated; severe increase in ostomy output compared to baseline; limiting self care ADL	Life-threatening consequences; urgent intervention indicated	Death
Definition: A disorder characterized by frequent and watery bowel movements.					

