Pancreatitis	-	Enzyme elevation or radiologic findings only	Severe pain; vomiting; medical intervention indicated (e.g., analgesia, nutritional support)	Life-threatening consequences; urgent intervention indicated	Death

Gastrointestinal disorders					
Adverse Event	Grade				
	1	2	3	4	5
Definition: A disorder characterized by inflammation of the pancreas.					
Periodontal disease	Gingival recession or gingivitis; limited bleeding on probing; mild local bone loss	Moderate gingival recession or gingivitis; multiple sites of bleeding on probing; moderate bone loss	Spontaneous bleeding; severe bone loss with or without tooth loss; osteonecrosis of maxilla or mandible	-	-
Definition: A disorder in the gingival tissue around the teeth.					
Peritoneal necrosis	-	-	Tube feeding or TPN indicated; radiologic, endoscopic, or operative intervention indicated	Life-threatening consequences; urgent operative intervention indicated	Death
Definition: A disorder characterized by a necrotic process occurring in the peritoneum.					
Proctitis	Rectal discomfort, intervention not indicated	Symptoms (e.g., rectal discomfort, passing blood or mucus); medical intervention indicated; limiting instrumental ADL	Severe symptoms; fecal urgency or stool incontinence; limiting self care ADL	Life-threatening consequences; urgent intervention indicated	Death
Definition: A disorder characterized by inflammation of the rectum.					
Rectal fistula	Asymptomatic; clinical or diagnostic observations only; intervention not indicated	Symptomatic; altered GI function	Severely altered GI function; TPN or hospitalization indicated; elective operative intervention indicated	Life-threatening consequences; urgent intervention indicated	Death
Definition: A disorder characterized by an abnormal communication between the rectum and another organ or anatomic site.					
Rectal hemorrhage	Mild; intervention not indicated	Moderate symptoms; medical intervention or minor cauterization indicated	Transfusion, radiologic, endoscopic, or elective operative intervention indicated	Life-threatening consequences; urgent intervention indicated	Death
Definition: A disorder characterized by bleeding from the rectal wall and discharged from the anus.					
Rectal mucositis	Asymptomatic or mild symptoms; intervention not indicated	Symptomatic; medical intervention indicated; limiting instrumental ADL	Severe symptoms; limiting self care ADL	Life-threatening consequences; urgent operative intervention indicated	Death

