**13.5 Appendix 5: Acute Radiation Morbidity Scoring Criteria (RTOG)**

	[ 0 ]	[ 1 ]	[ 2 ]	[ 3 ]	[ 4 ]
SKIN	No change over baseline	Follicular, faint or dull erythema/ epilation/dry desquamation/ decreased sweating	Tender or bright erythema, patchy moist desquamation/ moderate edema	Confluent, moist desquamation other than skin folds, pitting edema	Ulceration, hemorrhage, necrosis
UPPER G.I.	No change	Anorexia with <=5% weight loss from pretreatment baseline/ nausea not requiring antiemetics/ abdominal discomfort not requiring parasympatholytic drugs or analgesics	Anorexia with <=15% weight loss from pretreatment baseline/nausea &/ or vomiting requiring antiemetics/ abdominal pain requiring analgesics	Anorexia with >15% weight loss from pretreatment baseline or requiring N-G tube or parenteral support. Nausea &/or vomiting requiring tube or parenteral support/abdominal pain, severe despite medication/hematemesis or melena/ abdominal distention (flat plate radiograph demonstrates distended bowel loops)	Ileus, subacute or acute obstruction, perforation, GI bleeding requiring transfusion/abdominal pain requiring tube decompression or bowel diversion
LOWER G.I. INCLUDING PELVIS	No change	Increased frequency or change in quality of bowel habits not requiring medication/ rectal discomfort not requiring analgesics	Diarrhea requiring parasympatholytic drugs (e.g., Lomotil)/ mucous discharge not necessitating sanitary pads/ rectal or abdominal pain requiring analgesics	Diarrhea requiring parenteral support/ severe mucous or blood discharge necessitating sanitary pads/abdominal distention (flat plate radiograph demonstrates distended bowel loops)	Acute or subacute obstruction, fistula or perforation; GI bleeding requiring transfusion; abdominal pain or tenesmus requiring tube decompression or bowel diversion

	[ 0 ]	[ 1 ]	[ 2 ]	[ 3 ]	[ 4 ]
GENITOURINARY	No change	Frequency of urination or nocturia twice pretreatment habit/ dysuria, urgency not requiring medication	Frequency of urination or nocturia which is less frequent than every hour. Dysuria, urgency, bladder spasm requiring local anesthetic (e.g., Pyridium)	Frequency with urgency and nocturia hourly or more frequently/ dysuria, pelvis pain or bladder spasm requiring regular, frequent narcotic/gross hematuria with/ without clot passage	Hematuria requiring transfusion/ acute bladder obstruction not secondary to clot passage, ulceration or necrosis

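### Attribution to chemoradiation decides an adverse event's grading scale and capture window, which conflicts with a primary endpoint covering all events on CTCAE

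*Combined protocol and SAP*

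**What the plan says.** Several sections bear on how a toxicity is graded, and they do not agree.

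- **6.2.4.1** divides events by cause. For chemoradiation: "Assessment of systemic reaction/toxicity/side effects of standard (chemoradiation) therapy will be collected at specified visits and be reported using the" RTOG acute criteria of Appendix 5. For the rest: "all other adverse events will be collected from the time of informed consent through discharge and will be assessed using the CTCAE v4.03".
- **9.3.1** uses the same division for capture. Events due to chemoradiation are reported from its start to the Week 4 visit; all other events are reported from consent to the end of the study.
- **7.1.3** offers the scales as alternatives. Grades follow CTCAE "for reporting of all serious adverse events (SAE) or the Acute Radiation Morbidity Scoring Criteria (RTOG"), with no rule for choosing.
- **Section 3, primary endpoint 1** covers all adverse events, with CTCAE v4.03 named for severity. **Endpoint 3** covers chemoradiation side effects on RTOG.
- **7.1.1** has all adverse events recorded from screening throughout the study. **7.1** names CTCAE v4.03 for the safety of INO-3112.
- **7.3** has the RTOG form completed for each patient at specified visits. **8.2** has data from both scales recorded for each patient at each visit.
- **7.2** makes the investigator judge the relation to INO-3112. It defines no categories for attribution to chemoradiation.
- **4.4** states: "If the subject manifests Grade 4 toxicity attributable to study treatment/EP, she will not receive further study treatment/EP". For attributable Grade 3 toxicity it requires a discussion about continuing. It names no scale. Neither do 7.5.3.3 and 7.5.3.4.

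**The concern.** The primary objective is to judge the toxicity of INO-3112 against what standard therapy alone would produce. In Cohort 1 the first dose comes within 2 weeks of the end of chemoradiation, so the cause of an early gastrointestinal, genitourinary or hematologic event will often be uncertain. Under 6.2.4.1 that uncertain judgement, made by an unblinded investigator without defined categories, selects the scale. Under 9.3.1 it also selects how long the event is collected.

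If the scales graded such events alike, little would follow. Where they differ, the severe-event rows of a primary safety table depend on an opinion about cause, which a safety table should keep apart from severity. The documents also give no rule for an event with mixed attribution, or for one that appears on both forms.

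**Working it through.** **1. The plan's own figures (8.1).** Inputs: a reference rate of 23% for Grade 3 or 4 hematologic toxicity, and n = 10.

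- Chance of at least one event: 1 − 0.77^10 = 1 − 0.0733 = 92.7%, consistent with the stated figure of about 92%.
- Upper limit for 0/10, two-sided exact 95%: 1 − 0.025^(1/10) = 30.8%, consistent with the stated limit below 31%.

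Both come from the 23% and n alone, so the choice of scale does not alter them. Section 8.1 does not say which scale lies behind the 23%.

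**2. The two scales compared.** RTOG is from Appendix 5, CTCAE from Appendix 4.

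| Event | RTOG | CTCAE |
|---|---|---|
| Rectal bleeding, transfused | 4 | 3 |
| Hematuria, transfused | 4 | 3 |
| Hemoglobin 7.5 to <8.0 g/dL, no transfusion | 2 | 3 |
| At least 7 stools/day over baseline, controlled with Lomotil | 2 | 3 |
| Hourly urinary frequency with urgency and nocturia | 3 | at most 2 (urinary frequency) |
| White cells, neutrophils, platelets: numeric cut-offs for Grades 2 to 4 | same | same |

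Key definitions:

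- RTOG Grade 4 for the lower GI tract includes "GI bleeding requiring transfusion; abdominal pain or tenesmus requiring tube decompression or bowel diversion". CTCAE Grade 3 for rectal hemorrhage reads "Transfusion, radiologic, endoscopic, or elective operative intervention indicated".
- CTCAE Grade 3 diarrhea begins "Increase of >=7 stools per day over baseline; incontinence; hospitalization indicated". RTOG puts diarrhea needing parasympatholytic drugs at Grade 2 and reserves Grade 3 for parenteral support.
- CTCAE Grade 3 anemia is "Hgb <8.0 g/dL; <4.9 mmol/L; <80 g/L; transfusion indicated". RTOG Grade 2 runs from below 9.5 down to 7.5 g/dL. Red-cell transfusion for anemia is Grade 3 on both.

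The differences are therefore specific to certain items. They run in both directions and cross both the 2/3 and the 3/4 boundary.

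**3. Capture.** Read literally, 9.3.1 leaves a non-serious event that begins after Week 4 and is put down to chemoradiation outside both windows. Serious events are still collected, because 9.3.2 disregards causality. Table 1 also ends the chemo/RT row at Week 4, but 6.1.2 lists that assessment at Weeks 2, 6, 10 and 14.

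**4. Size.** Section 8.2 specifies exact Clopper-Pearson intervals. With n = 10, one woman is 1/10 = 10 percentage points.

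- 0/10: 0 to 30.8%
- 1/10: 0.3 to 44.5%
- 2/10: 2.5 to 55.6%

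For example, one woman with hemoglobin 7.7 g/dL and no transfusion makes the Grade 3/4 anemia row 1/10 on CTCAE and 0/10 on RTOG.

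**5. The Grade 3/4 rules.** Each requires attribution to study treatment.

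- Events requiring expedited reporting (7.5.2, which feeds 7.5.3.1) are tied to CTCAE, with Table 6.1 for injection sites. 7.5.3.5 also names CTCAE.
- 7.5.3.2 is worded by seriousness, threat to life or death, not by a grade number.
- That leaves 4.4, 7.5.3.3 and 7.5.3.4. The scale matters there only for an event judged at least possibly related to study treatment but scored as a chemoradiation effect. A transfused rectal bleed of that kind is Grade 3 or Grade 4 under 4.4, depending on the form used.

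**The case against.** The best case for the plan is that RTOG is an additional scheduled form and not a diversion. Section 7.3 has it completed for each patient, 8.2 speaks of both scales for each patient, Table 1 keeps separate rows for chemo/RT effects and adverse events, and endpoint 1 covers all events. On that reading an event attributed to chemoradiation is also graded on CTCAE and never leaves endpoint 1. This is a live reading, and it is why the documents cannot be said to establish a strict either/or. It does not dispose of the point. Sections 6.2.4.1 and 9.3.1 state the split by cause in plain terms, 8.2 does not say that the same event receives two grades, and no rule says which grade feeds which table.

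A reader might also infer four stronger claims that the documents do not support:

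- **That the scales disagree generally.** White-cell, neutrophil and platelet cut-offs coincide at Grades 2 to 4.
- **That the Grade 3/4 rules as a whole turn on the scale.** They turn on relatedness to study treatment. An event attributed only to chemoradiation is outside them on either scale, and 7.1 points to CTCAE for the safety of INO-3112.
- **That Cohort 2 is handled differently.** Section 6.2.4.1 names chemoradiation, but no passage sends salvage-therapy effects to a different table, and 7.3 refers to each patient.
- **That the calculation in 8.1 is undermined.** Its figures do not depend on the scale.

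It is also fair to say that the intervals show what one reclassified woman does, not how often reclassification would occur. The documents give no basis for that frequency.

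**Conclusion.** The point holds as a conflict within the protocol that reaches a primary safety endpoint. Sections 6.2.4.1 and 9.3.1 let attribution to chemoradiation choose the scale and the collection period, and 7.1.3 leaves the choice open. Endpoint 1 and 7.1.1 require all events, and endpoint 1 requires CTCAE severity. For the listed items the consequence is one grade in either direction, or absence from the CTCAE table. Each affected woman moves a severe-event row by 10 percentage points.

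This rests on two assumptions: that some events have uncertain cause, which the short gap before Day 0 makes plausible, and that sites follow the literal wording of 6.2.4.1. If every event is in practice graded on both scales, what remains is double grading without a tabulation rule. The effect on the discontinuation and pausing rules is confined to the mixed-attribution events described above.

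**What to change.** - **6.2.4.1, 7.1.3 and 9.3.1:** record every adverse event from consent to the end of the study, and grade it on CTCAE v4.03 for endpoint 1 whatever its attribution. Record attribution as a separate field.
- **Endpoint 3:** keep RTOG as an additional score for this endpoint. Bring the visits listed in 6.1.2 into line with Table 1.
- **8.2:** state that the CTCAE and RTOG tables overlap and are not summed.
- **4.4, 7.5.3.3 and 7.5.3.4:** reconcile these with 7.1 and 7.1.3 on which scale their grades refer to. Which clinical rule should apply is for the sponsor and the investigators.

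Clarifying 8.2 alone would not be enough. An event scored only on RTOG has no CTCAE grade to tabulate, and one not collected after Week 4 cannot be recovered.

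The cost is protocol wording and possibly one extra CRF field. The adverse event table becomes longer because expected chemoradiation effects appear in it.

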##### **6.2.4.2 Physical Assessments**

A full examination including complete gynecological exam and ECOG performance status will be conducted during screening and study discharge. A targeted physical assessment (including ECOG performance) will be performed at other visits as determined by the Investigator or directed per subject complaints.

